6.7.2 Guidelines for Evaluation of Measurable Disease

General Aspects of Tumor Measurement - All measurements should be taken and recorded in metric notation using a ruler or calipers. All baseline evaluations should be performed as closely as possible to the beginning of treatment and never more than 4 weeks before the beginning of the treatment. Note: Tumor lesions that are situated in a previously irradiated area might or might not be considered measurable. The same method of assessment and the same technique should be used to characterize each identified and reported lesion at baseline and during follow-up. Imaging-based evaluation is preferred to evaluation by clinical examination when both methods have been used to assess the anti-tumor effect of a treatment.

Specific Methods of Tumor Measurement:

- **Clinical lesions** – Clinical lesions will only be considered measurable when they are superficial (e.g., skin nodules and palpable lymph nodes). In the case of skin lesions, documentation by color photography, including a ruler to estimate the size of the lesion, is recommended.
- **Chest x-ray** – Lesions on chest x-ray are acceptable as measurable lesions when they are clearly defined and surrounded by aerated lung. However, CT is preferable.
- **Conventional CT and MRI** – This guideline has defined measurability of lesions on CT scan based on the assumption that CT slice thickness is 5mm or less. If CT scans have slice thickness greater than 5mm, the minimum size for a measurable lesion should be twice the slice thickness. MRI is also acceptable in certain situations (e.g. for body scans).

Use of MRI remains a complex issue. MRI has excellent contrast, spatial, and temporal resolution; however, there are many image acquisition variables involved in MRI, which greatly impact image quality, lesion conspicuity, and measurement. Furthermore, the availability of MRI is variable globally. As with CT, if an MRI is performed, the technical specifications of the scanning sequences used should be optimized for the evaluation of the type and site of disease. Furthermore, as with CT, the modality used at follow-up should be the same as was used baseline and the lesions should be measured/assessed on the same pulse sequence. It is beyond the scope of the RECIST guidelines to prescribe specific MRI pulse sequence parameters for all scanners, body parts, and diseases. Ideally, the same type of scanner should be used and the image acquisition protocol should be followed as closely as possible to prior scans. Body scans should be performed with breath-holding scanning techniques, if possible.

- **PET-CT** – At present, the low dose or attenuation correction CT portion of a combined PET-CT is not always of optimal diagnostic CT quality for use with RECIST measurements. However, if the site can document that the CT performed as part of a PET-CT is of identical diagnostic quality to a diagnostic CT (with IV and oral contrast), then the CT portion of the PET-CT can be used for RECIST measurements and can be used interchangeably with conventional CT in accurately measuring cancer lesions over time.

Note, however, that the PET portion of the CT introduces additional data which may bias an investigator if it is not routinely or serially performed.

- Ultrasound (US) – Ultrasound is not useful in assessment of lesion size and should not be used as a method of measurement. Ultrasound examinations cannot be reproduced in their entirety for independent review at a later date, and, because they are operator dependent, it cannot be guaranteed that the same technique and measurements will be taken from one assessment to the next. If new lesions are identified by ultrasound in the course of the study, confirmation by CT or MRI is advised. If there is concern about radiation exposure at CT, MRI may be used instead of C in selected instances.

- Endoscopy, Laparoscopy – The utilization of these techniques for objective tumor evaluation is not advised. However, such techniques can be useful to confirm complete pathological response when biopsies are obtained or to determine relapse in trials where recurrence following complete response (CR) or surgical resection is an endpoint.

- Tumor Markers – Tumor markers alone cannot be used to assess response. If markers are initially above the upper normal limit, they must normalize for a patient to be considered in complete clinical response.

- Cytology, Histology – These techniques can be used to differentiate between partial responses (PR) and complete responses (CR) in rare cases (e.g., residual lesions in tumor types, such as germ cell tumors, where known residual benign tumors can remain). The cytological confirmation of the neoplastic origin of any effusion that appears or worsens during treatment when the measurable tumor has met criteria for response or stable disease is mandatory to differentiate between response or stable disease (an effusion may be a side effect of the treatment) and progressive disease.

-FDG-PET – While FDG-PET response assessments need additional study, it is sometimes reasonable to incorporate the use of FDG-PET scanning to complement CT scanning in assessment of progression (particularly possible “new” disease). New lesions on the basis of FDG-PET imaging can be identified according to the following:

- a. Negative FDG-PET at baseline, with a positive FDG-PET at follow-up is a sign of PD based on a new lesion.
- b. No FDG-PET at baseline and a positive FDG-PET at follow-up: If the positive FDG-PET at follow-up corresponds to a new site of disease confirmed by CT, this is PD. If the positive FDG-PET at follow-up is not confirmed as a new site of disease on CT, additional follow-up CT scans are needed to determine if there is truly progression occurring at that site (if so, the date of PD will be the date of the initial abnormal FDG-PET scan). If the positive FDG-PET at follow-up corresponds to pre-existing site of disease on CT that is not progressing on the basis of the anatomic images this is not PD.
- c. FDG-PET may be used to upgrade a response to a CR in a manner similar to a biopsy in cases where a residual radiographic abnormality is thought to represent fibrosis or scarring. The use of FDG-PET in this circumstance should be prospectively described in the protocol and supported by disease-specific medical literature for the indication. However, it must be acknowledged that both approaches may lead to false positive CR due to limitations of FDG-PET and biopsy resolution/sensitivity.

Note: A “positive” FDG-PET scan lesion means one which is FDG avid with uptake greater than twice that of the surrounding tissue on the attenuation corrected image.

6.7.3 Response Criteria

6.7.3.1 Evaluation of Target Lesions

- **Complete Response (CR):** Disappearance of all target lesions. Any pathological lymph nodes (whether target or not) must have reduction in short axis to < 10mm.
- **Partial Response (PR):** At least a 30% decrease in the sum of the longest diameter (LD) of target lesions, taking as reference the baseline sum diameters.
- **Progressive Disease (PD):** At least a 20% increase in the sum of the diameters of target lesions, taking as reference the smallest sum on study (this included the baseline sum if that is the smallest on study). In addition to the relative increase of 20%, the sum must also demonstrate an absolute increase of at least 5mm. (Note: the appearance of one or more new lesions is also considered progression.)
- **Stable Disease (SD):** Neither sufficient shrinkage to qualify for PR nor sufficient increase to qualify for PD, taking as reference the smallest sum diameters while on study.

6.7.3.2 Evaluation of Non-Target Lesions

- **Complete Response (CR):** Disappearance of all non-target lesions and normalization of tumor marker level. All lymph nodes must be non-pathological in size (<10mm short axis). Note: If serum CA27.29 levels are initially above the upper normal limit, they must normalize for a patient to be considered in complete clinical response.
- **Non-CR/Non-PD:** Persistence of one or more non-target lesion(s) and/or maintenance of tumor marker level above the normal limits.
- **Progressive Disease (PD):** Appearance of one or more new lesions and/or unequivocal progression of existing non-target lesions. Unequivocal progression should not normally trump target lesion status. It must be representative of overall disease status change, not a single lesion increase.
Although a clear progression of “non-target” lesions only is exceptional, in such circumstances the opinion of the treating physician should prevail, and the progression status should be confirmed at a later time by the review panel (or study chair).

6.7.4 Evaluation of Best Overall Response

The best overall response is the best response recorded from the start of the treatment until disease progression/recurrence (taking as reference for progressive disease the smallest measurements recorded since the treatment started). The patient's best response assignment will depend on the achievement of both measurement and confirmation criteria.

For Patients with Measurable Disease (i.e., Target Disease)				
Target Lesions	Non Target Lesions	New Lesions	Overall Response	Best Overall Response when Confirmation is Required*
CR	CR	No	CR	\geq 4 wks. confirmation**
CR	Non-CR/Non-PD	No	PR	\geq 4 wks. confirmation**
CR	Not evaluated	No	PR	
PR	Non-CR/Non-PD/not evaluated	No	PR	
SD	Non-CR/Non-PD/not evaluated	No	SD	Documented at least once \geq 4 wks. from baseline**
PD	Any	Yes or No	PD	No prior SD, PR or CR
Any	PD***	Yes or No	PD	
Any	Any	Yes	PD	

* See RECIST 1.1 manuscript for further details on what is evidence of a new lesion.
 ** Only for non-randomized trials with response as primary endpoint.
 *** In exceptional circumstances, unequivocal progression in non-target lesions may be accepted as disease progression.

Note: Patients with a global deterioration of health status requiring discontinuation of treatment without objective evidence of disease progression at that time should be reported as "symptomatic deterioration". Every effort should be made to document the objective progression even after discontinuation of treatment.

For Patients with Non-Measurable Disease

(i.e., Non-Target Disease)

Non-Target Lesions	New Lesions	Overall Response
CR	No	CR
Non-CR/non-PD	No	Non-CR/non-PD*
Not all evaluated	No	Not evaluated
Uequivocal PD	Yes or No	PD
Any	Yes	PD

* "Non-CR/non-PD" is preferred over "stable disease" for non-target disease since SD is increasingly used as an endpoint for assessment of efficacy in some trials so to assign this category when non-lesions can be measured is not advised.

6.7.5 Duration of Response

Duration of Overall Response – The duration of overall response is measured from the time measurement criteria are met for CR or PR (whichever is first recorded) until the first date that recurrent or progressive disease is objectively documented (taking as reference for progressive disease the smallest measurements recorded since the treatment started). The duration of overall CR is measured from the time measurement criteria are first met for CR until the first date that recurrent disease is objectively documented.

Duration of stable disease – Stable disease is measured from the start of treatment until the criteria for progression are met, taking as reference the smallest measurements recorded since the treatment started, including the baseline measurements.

6.7.6 Definitions Related to Evaluation Unrelated to Objective Response

Overall Survival is the observed length of life from entry into the study to death or the date of last contact.

Progression-Free Survival is the period from study entry until disease progression, or death, whichever occurs first.

Recurrence-Free Survival (non-measurable disease studies) is the period from study entry until disease recurrence, death or date of last contact.

Subjective Parameters including performance status, specific symptoms, and side effects.

Side effects are graded according to the National Cancer Institute (NCI) Common Terminology Criteria for Adverse Events (CTCAE) version 4.03 (see Appendix A). Any patient who receives treatment on this protocol will be evaluated for toxicity. Each patient will be assessed periodically according to the study parameters table for the development of any toxicity. Dose modifications will be made based on toxicities as described earlier.

7.0 STATISTICAL CONSIDERATIONS

This is an open-label, single arm, single institution, pilot clinical trial. The primary objective is to characterize the safety profile and treatment tolerance of Veliparib (ABT-888) in combination with Lapatinib (Tykerb) in patients with metastatic, estrogen receptor (ER) negative, progesterone receptor (PR) negative, and human epidermal growth factor receptor 2 (HER-2-Neu) negative breast cancer. Secondary objectives will estimate the objective response rate (ORR) (complete responses [CRs] plus partial responses [PRs]); Determine progression free survival (PFS); correlate pre-treatment tumor gene expression profile, biomarkers of DNA repair (H2AX, BRCA localization), EGFR location and signaling, and apoptosis markers with the ORR and PFS; Correlate serial measures of CTCs and serum levels of M30 with the ORR and PFS and determine the pharmacokinetics of Veliparib and Lapatinib when given in combination. A total of 20 (maybe 25 if an additional cohort is added) patients will be enrolled in a single site (University of Alabama at Birmingham) over a projected 12-18 months accrual interval.

7.1 Primary Endpoint

We will characterize the safety profile and treatment tolerance of Veliparib (ABT-888) in combination with Lapatinib (Tykerb). Drug related toxicities for the safety analysis are defined as (see section 3.0 also): a) any grade 3 or 4 non-hematologic toxicity except alopecia, and nausea which is not refractory to anti-emetics; b) failure to recover to baseline (except alopecia) after delaying the next dose by more than 14 days; c) grade 3 or 4 neutropenia complicated by fever $\geq 38.5^{\circ}\text{C}$ or infection, or grade 4 neutropenia of a least 7 days duration; or d) grade 4 thrombocytopenia, or grade 3 thrombocytopenia complicated by hemorrhage. Toxicity evaluation of the patients enrolled in the trial will be done using the NCI Common Toxicity Criteria, Version 4.0).

7.2 Secondary Endpoint

In patients with metastatic TNBC, who will be treated with the combination of Veliparib and Lapatinib, we will estimate the ORR (CRs plus PRs); determine PFS; correlate pre-treatment tumor gene expression profile, biomarkers of DNA repair (H2AX, BRCA localization), EGFR location and signaling, and apoptosis markers with the ORR and PFS; correlate serial measures of CTCs and serum levels of M30 with the ORR and PFS; determine the pharmacokinetics of Veliparib and Lapatinib when given in combination.

7.3 Stratification

No Stratification will be incorporated in this pilot study.

7.4 Sample Size and Power Justification

This is a single arm pilot study to evaluate the safety of combination of Veliparib and Lapatinib in patients with metastatic TNBC. A total of 20 patients will be enrolled to evaluate the safety as treatment related toxicity rate and the objective response rate. The sample size is NOT determined by the statistical power but the feasibility and relative precision of estimate, e.g. standards error of the estimation is $\leq 10\%$. Assuming the acceptable toxicity rate with combination therapy is no more than 30%; then, we will be able to have two sided 95% exact confidence intervals ([Clopper-Pearson intervals](#)) of toxicity estimate from 11.8% to 54.3%. Meantime, this sample size will provide two-sided 95% exact confidence intervals ([Clopper-Pearson intervals](#)) of objective response rate estimation as follow:

Table 2 Exact 95% Confidence Interval for Response Rate Estimation

Response rate %	Confidence interval (lower) %	Confidence interval (Upper) %
20	5.73	43.66
25	8.66	49.10
30	11.89	54.28

If the response rate is equal or greater than 30%, we will propose a phase II trial to be conducted in the Translational Breast Cancer Research Consortium (TBCRC).

7.5 Analysis plan

We will consider that any subjects enrolled to the study as intent-to-treat (ITT) population; patients must at least start therapy or they will be replaced. The ITT patients will be included for all efficacy analysis. We will consider any patients who received at least one dose of Lapatinib and/or Veliparib as safety analysis population. The safety analysis population will be used for safety evaluation. The final statistical analysis will be conducted after all patients that have completed treatment with documentation of toxicity, response and progression free survival.

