This rule will provide a probability of 0.10 of stopping early if the true toxicity rate is 30%. In that case the expected number of subjects on the trial will be 18.87 and the expected number of toxicities will be 5.7. If, on the other hand, the true toxicity rate is 60%, then the probability of stopping early is 0.87 with an expected sample size of 9.8 and 5.9 expected toxicities. Table 2 is the stopping guideline if 'X' out of 'N' has a pre-defined toxicity. As an example, if we enroll 3 patients and all have toxicity, then we will consider stopping the trial; if we enroll 6 patients and 5 patients have toxicity then the trial will be stopped.

Drug related toxicities for the safety analysis described above are defined as: a) any grade 3 or 4 non-hematologic toxicity except anorexia, alopecia, nausea, fatigue, fever without neutropenia; b) failure to recover to baseline (except alopecia) after delaying the next dose by more than 14 days; c) grade 3 or 4 neutropenia complicated by fever $\geq 38.5^0$ C or infection, or grade 4 neutropenia of at least 7 days duration; or d) grade 4 thrombocytopenia, or grade 3 thrombocytopenia complicated by hemorrhage. Toxicity evaluation of the patients enrolled in the trial will be done using the NCI Common Toxicity Criteria, Version 4.0, and will be presented to the Clinical Protocol Monitoring Committee (UAB Safety and Monitoring Plan).

If toxicity meets the stopping rule at any time during the first 5 patients enrolled in the pilot study (see table 2), the protocol will allow the investigators to open a new 20 patient cohort using Lapatinib 1000 mg PO a day and Veliparib 150 mg PO twice a day. The new cohort will follow the same rules used in the original cohort (Cohort -1). Patients developing grade 1 and 2 toxicities will be permitted to take a drug holiday of up to 14 days; after the drug holiday, if the adverse event has resolved to the satisfaction of the investigator, the study drugs may be resumed at the same level. In the event of recurrent toxicity, there will be one dose reduction permitted (dose reduction minus one will be Lapatinib 750 mg PO daily continuously and Veliparib 100 mg PO every 12 hours continuously). If the adverse event recurs after dose reduction two, the patient will be taken off the study.

Patient Selection Criteria

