6.2 Pilot Trial

Twenty patients evaluable for response will be entered into this phase pilot trial; they will receive Lapatinib (1250 mg a day continuously for 28 days) in combination with Veliparib 200 mg every 12 hours for 28 consecutive days, starting on Day 2 Cycle 1). No blinding will be used in this study. Patients will be evaluated for response every 2 courses (every 8 weeks) according to the RECIST criteria version 1.1 (see Appendix D). Treatment will be administered on an outpatient basis. Treatment may continue without interruption in patients with CR, PR or SD until progression of the disease or unacceptable toxicity. Patients cannot receive any other concomitant therapy: chemotherapy, targeted therapy, radiation therapy, or other investigational agent while participating in the study. There are some restrictions on concomitant medications which must be recorded (see Appendix H). Patients may receive bisphosphonates; however, if used, bone lesions may not be used for progression or response. Patient with PD at any time will be taken off the study.

Investigators will maintain a confidential screening log of all potential study candidates that includes limited information about the patients (initials, sex, age), date, and outcome of screening process: enrolled in the study, reason for ineligibility or refused to participate. Investigators will be expected to maintain an enrollment log for all patients enrolled in the study indicating their assigned study number. A patient will be considered enrolled upon assignment of a patient number. Each patient will sign an informed consent provided by the site.

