6.7 Efficacy and Safety Assessments

Response and progression will be evaluated in this study using the international criteria proposed by the Response Evaluation Criteria in Solid Tumors (RECIST) Committee; version 1.1 (see Appendix D).⁷⁵ Changes in only the largest diameter (unidimensional measurement) of the tumor lesions are used in the RECIST criteria. Note: Lesions are either measurable or non-measurable using the criteria provided below. The term “evaluable” in reference to measurability will not be used because it does not provide additional meaning or accuracy.

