7.5.1 Analysis of Safety

The primary analysis is of safety that will include any patients who receive at least one dose of Lapatinib and/or Veliparib. The treatment related toxicity rate will be estimated at the end of the study along with two sided 95% exact confidence intervals ([Clopper-Pearson intervals](#)). Analysis of safety data will be descriptive. Descriptive statistics will be calculated for quantitative safety data and frequency counts will be compiled for classification of qualitative safety data. Adverse event and serious adverse event (AE/SAE) (AE/SAE definition is in 9.1.1) reporting during the study will be summarized by relationship to study drug and intensity. Number and proportion of adverse event, serious adverse event and grade 3 or 4 lab toxicity will be reported by body system and by each study arm. Patient's baseline lab data and its change during treatment at each visit will be presented. Graphic statistics tool such as box plot will be used when it is appropriate.

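### The 10% standard error behind n=20 is missed at the plan's own 30% rate, the toxicity rate and ORR are not split by starting-dose cohort, and the ORR denominator needs reconciling

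*Combined protocol and SAP*

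**What the plan says.** **Precision.** Section 7.4 bases n=20 on feasibility and precision rather than power, and gives a standard error of 10% or less as its example. It prints exact 95% intervals for response rates of 20%, 25% and 30%, and one for a toxicity rate of 30%.

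**Cohorts.** Section 3.0 says that if the stopping rule is met within the first five patients, "the protocol will allow the investigators to open a new 20 patient cohort" at lower starting doses. Section 7.0 then puts the total at possibly 25. Section 7.5.1 states: "The primary analysis is of safety that will include any patients who receive at least one dose of Lapatinib and/or Veliparib". It plans a toxicity rate with an exact interval at the end of the study, and section 7.5.2 plans an ORR for the combination group. Two outputs are split: counts of adverse events, serious adverse events and grade 3 or 4 laboratory toxicity by study arm (7.5.1), and pharmacokinetics by dose group (7.5.3).

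**Denominator.** Section 7.5 takes as its ITT set "any subjects enrolled to the study as intent-to-treat (ITT) population; patients must at least start therapy or they will be replaced", and adds: "The ITT patients will be included for all efficacy analysis". Section 6.2 says: "A patient will be considered enrolled upon assignment of a patient number". It also says: "Twenty patients evaluable for response will be entered into this phase pilot trial". Sections 3.0, 7.4 and 7.7 instead set the target at 20 enrolled. Section 7.4 attaches a consequence to the result without naming a population or cohort: "If the response rate is equal or greater than 30%, we will propose a phase II trial".

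**The concern.** The standard error is the only numerical precision target given for the sample size, so it should hold at the rate on which the plan relies.

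The toxicity rate is the primary analysis. A lower-dose cohort opens only because the first few patients had too many toxicities. If those patients stay in the same rate as the new cohort, the headline estimate is weighted towards the result that caused the change of dose, and it belongs to no regimen that a later trial would use.

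For the ORR, the 30% criterion falls exactly on 6 of 20, so a single disputed patient decides whether it is met. If membership of the denominator is not fixed in advance, it may be settled after the responses are known.

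**Working it through.** **Precision.** Inputs from section 7.4: n=20; rates of 20%, 25% and 30%. I read the 10% as percentage points on the rate.

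The plan's own intervals reproduce. Clopper-Pearson gives 5.73–43.66 for 4/20, 8.66–49.10 for 5/20 and 11.89–54.28 for 6/20. The toxicity lower limit printed as 11.8 is 11.89 truncated.

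SE = √(p(1−p)/20):

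| Rate | Calculation | SE |
|---|---|---|
| 20% | √(0.16/20) | 8.9% |
| 25% | √(0.1875/20) | 9.7% |
| 30% | √(0.21/20) | 10.25% |
| 50% (maximum) | √(0.25/20) | 11.2% |

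An SE of at most 0.10 needs p(1−p) ≤ 20 × 0.01 = 0.20. That means p ≤ (1 − √0.2)/2 = 0.276, or p ≥ 0.724. The target therefore holds at two of the three tabulated rates and fails at 30%.

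**Cohorts.** Inputs: the boundary table in sections 3.0 and 7.6. Its stated properties reproduce: probability of stopping 0.098 at 30% true toxicity and 0.872 at 60% (plan: 0.10 and 0.87); expected sample size 18.87 and 9.76 (plan: 18.87 and 9.8).

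Within five patients the boundary can first be met only at 3/3 or at 4/5, because 4/4 already contains 3/3. The probability is p³ + 3p⁴(1−p):

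- p = 0.30: 0.027 + 0.017 = 0.044
- p = 0.60: 0.216 + 0.156 = 0.372

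If the first cohort ends when the boundary is met, the two cohorts total 23 or 25. With an assumed 6/20 toxicities in the second cohort:

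| | First cohort | Second cohort | One rate |
|---|---|---|---|
| Trigger at 3/3 | 100% (29.2–100) | 30% (11.9–54.3) | 9/23 = 39% (19.7–61.5) |
| Trigger at 4/5 | 80% (28.4–99.5) | 30% (11.9–54.3) | 10/25 = 40% (21.1–61.3) |

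**Denominator.** A patient is enrolled once a number is assigned, which need not coincide with a first dose. On the literal ITT wording, a patient who never starts stays in the denominator and the replacement is added to it. On the other reading of the same sentence, the replaced patient drops out. With six responders:

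- 6/20 = 30.0%: criterion met
- 6/21 = 28.6%: criterion not met; 7 of 21 would be needed

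The documents give no rate of never starting. For assumed rates of 2%, 5% or 10%, the chance of at least one non-starter before 20 are treated is 1 − (1−q)²⁰ = 0.33, 0.64 or 0.88.

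**The case against.** Several points on the other side stand. No section says that cohorts will be pooled. Section 3.0 speaks of a new cohort run under the same rules as the original, and every interval in 7.4 is at n=20, so per-cohort estimation may well be intended. The by-arm tables in 7.5.1 could be stretched to mean cohort, although they cover event and laboratory counts and not the toxicity rate, the ORR or the 30% criterion. The second cohort is optional, and its trigger is unlikely if toxicity is acceptable. The standard error is offered only as an example and misses by a quarter of a point. The ORR is secondary and its analysis descriptive. A replaced patient is ordinarily not counted among the 20.

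Four stronger readings are tempting but unsupported:

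- *Pooling in itself lowers the chance of meeting 30%.* At a true ORR of 30% in both cohorts, that chance is 0.58 at n=20, 0.56 at n=23 and 0.49 at n=25. The smallest passing results are 6/20 = 30.0%, 7/23 = 30.4% and 8/25 = 32.0%, so the gap is integer rounding and not bias. At n=30, where 9/30 is exactly 30%, the chance is 0.57.
- *Section 6.7 stops the evaluable patients of 6.2 from meaning patients with measurable disease.* Section 6.7 says that the term "in reference to measurability will not be used because it does not provide additional meaning or accuracy", but it is describing lesions. Measurable disease is an entry requirement in 4.1, so that reading of 6.2 remains open.
- *A result below 30% ends development.* The plan states no such rule, and sections 2.7 and 3.0 say without condition that the pilot data will be used to design a phase II trial.
- *Treated patients are the only correct ORR denominator.* The plan names ITT, and keeping replaced non-starters in it would remove the ambiguity equally well.

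**Conclusion.** The point holds as a minor one, in three parts.

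1. The standard error statement in 7.4 is wrong at the plan's 30% rate: 10.25% against at most 10%, with a maximum of 11.2%. This needs no outside assumption beyond reading the 10% as percentage points.
2. If the lower-dose cohort opens, the primary toxicity rate taken literally combines the triggering toxicities with the new cohort. The shift is from 30% to 39% or 40% under the assumed 6/20. It matters only in that event, whose trigger has probability 0.04 at 30% true toxicity and 0.37 at 60%. The ORR and the 30% criterion likewise have no stated cohort. This is an omission, not a declared plan to pool.
3. As a secondary point, sections 3.0, 6.2, 7.0, 7.4, 7.5 and 7.7 do not agree on the number or kind of patients to be entered, and 7.5 does not settle whether replaced non-starters count. One such patient is enough to turn a met criterion into an unmet one. How often this would happen cannot be derived from the documents.

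The toxicity denominator itself is clear (patients dosed), and the printed exact intervals are correct.

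**What to change.** - **Section 7.4:** restate the standard error as about 10.2% at a 30% rate and at most 11.2%. Leave the exact intervals as they are. The only cost is a slightly less favourable figure.
- **Sections 7.5.1 and 7.5.2:** report the toxicity rate and ORR with exact intervals by starting-dose cohort, with any pooled rate as supportive only. In 7.4, apply the 30% criterion by cohort. The intervals widen slightly: 6/20 spans 42.4 points, against 41.8 for 9/23 and 40.2 for 10/25. A first cohort of 3 to 5 says almost nothing alone, and the text should acknowledge this.
- **Sections 3.0, 6.2, 7.0, 7.4, 7.5 and 7.7:** reconcile the target number, define the evaluable patients of 6.2 or remove the term, and state whether replaced non-starters count in the ORR and the 30% criterion. Keeping them preserves ITT but lowers the rate. Excluding them departs from strict ITT and may flatter the result if non-starters have a worse prognosis, so they should then be listed separately. If the evaluable count was meant as the enrolment target, the number to enrol could change, and the sponsor must say which was intended.

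None of this alters dosing.
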